1.3.1 Justification for a protocol amendment

A decision was made to increase the initial frequency of dosing from once in █ weeks to once in █ weeks for at least the first █ cycles █
 █ The justification for this is discussed also in section 7.6 █
 █.

████████████████████ The most frequently recorded AEs were under the following Medical Dictionary for Regulatory Activities (MedDRA) system organ classes: infections and infestations, gastrointestinal disorders, general disorders and administration site conditions, and respiratory, thoracic and mediastinal disorders. This information is consistent with the safety profile of imetelstat according to the current version of the IB. A total of 30 SAEs were recorded in █████ patients, of which █████ were assessed as being at least possibly related to imetelstat. Of these █████ █████ were assessed as unexpected and were reported as SUSARs.

According to the safety data collected, no major change to the risk assessment was seen and there was no cause to conclude that imetelstat should not be used in patients with MDS/AML.

Given the short half-life of imetelstat, there is reason to believe that an increased frequency of dosing may be beneficial to patients

Given that no new safety signals to argue stopping imetelstat therapy were seen, the limited existence of treatment options and poor prognosis in this patient population, a decision was made to treat patients at a higher frequency of imetelstat administration for at least the first 12 cycles. There is a potential that neutropenia could be aggravated by the increased frequency of imetelstat. Therefore, the prophylactic use of antibiotics and antifungals has been recommended for use in patients according to local standards, especially when they are on the 1200 mg dosing. This prophylactic use of antimicrobials may also prevent infections as a reason for disease progression.

A risk benefit assessment will be performed after enrolling some patients as described in section 4.2.

Additional note:

The ongoing COVID-19 pandemic may affect the conduct and continuity of this clinical trial and may require implementation of temporary or alternative safety-related procedures or mechanisms. A designated guideline describing this mechanism will be provided to the participating sites and is part of the site training procedures.

Participation in this trial does not create specific risks for patients apart from the general risks of the COVID-19 pandemic. The IMP can solely be administered intravenously, making it impossible to dose patients at home. Therefore, patients will need to come to the clinic or stay in the hospital for treatment and staging procedures. All possible efforts will be made to avoid exposure to SARS-CoV2 during these study visits and site staff contacts.

Deviations from protocol enrollment criteria due to COVID-19 are neither planned nor granted. Deviations from planned study procedures in response to COVID-19 have to be documented as being related to COVID-19. All temporary mechanisms utilized will remain in effect only for the duration of the pandemic.

2 Objective of the study and endpoints

2.1 Primary objective(s)

The primary objective of the study is to

- assess the efficacy of imetelstat for the treatment of AML and MDS patients failing or being refractory to hypomethylating agent (HMA)-based treatment

2.2 Secondary and other objectives

Secondary objectives of the study are to further assess efficacy and safety of imetelstat regarding following measures

- Toxicity as measured by NCI CTCAE v5.0
- Overall survival
- Progression-free-survival
- Duration of overall response
- Best overall response
- Quality of life (EORTC QLQ-C30)

2.3 Study endpoints

2.3.1 Primary endpoint

The primary endpoint of the study is defined as overall hematological response rate as assessed in [REDACTED] of treatment with imetelstat.

All patients with one of the following responses assessed by samples and procedures taken/carried out at [REDACTED] are defined as responders (assessed through the combined response criteria for MDS and AML used in this trial (see Appendix III a), section 16.3):

[1] CR, CRi, PR as defined in Appendix III a)

[2] Hematologic improvement (for one or several lines) as defined in Appendix III a)

Response rate is calculated as follows: number of responders divided by the number of all patients of the analysis set. Patients for whom the overall hematologic response cannot be determined will be considered as treatment failures.

2.3.2 Secondary endpoints

The following secondary endpoints will be analyzed in this study.

Safety Measurements

- Toxicity as measured by NCI CTCAE v5.0

Efficacy Measurements

- Overall survival
 - defined as the time from the beginning of imetelstat treatment until death or censored at the date of the last follow-up visit.
- Progression-free-survival
 - defined as the duration of time from time of imetelstat treatment to time of progression or death, whichever occurs first. A subject who has neither progressed nor died will be censored on the date of last follow-up visit.
- Duration of best overall response
 - measured from the time measurement criteria are met for CR, CRi, PR or SD (whichever is first recorded, defined in Appendix III a)) until the first date at which recurrent or progressive disease is objectively documented.
- Best overall response
 - defined as the best response recorded from the start of the imetelstat treatment until disease progression (taking as reference for progressive disease the smallest measurements recorded since the treatment started).
- Response based on IWG 2023 criteria²⁴ (MDS population only)
 - assessed in [REDACTED] of treatment with imetelstat as:
 - Overall Response Rate (ORR) = CR (or CR equivalent)* + PR + CR_L + CR_h + HI, or
 - No response = Not meeting criteria for CR (or CR equivalent)*, PR, CR_L, CR_h, or HI.
 - For definition see Appendix III b).
- Scores of EORTC QLQ-C30 (version 3)
 - Global health status / QoL
 - Functional scales
 - Symptom scales / items

3 Translational program

Bone marrow and blood samples will be obtained at the indicated time points and stored for translational analyses, in particular assessment of response and measurable residual disease and identification of prognostic or predictive biomarkers. If adequate BM aspirate is not attainable, peripheral blood may be used if at least 5% or more BM blasts are present. If this is not the case, a BM biopsy will be required.

3.1 Genetic profiling

Somatic mutation profiling will be performed at baseline, at visit V9 (assessment of primary end point) and at EOT, using targeted NGS assay at the central laboratories. Additional available time points may be analyzed if necessary.

3.2 Measurable residual disease (MRD)

Analyses of measurable residual disease, using a targeted NGS approach with unique molecular identifiers, will be performed at the Leipzig laboratory (for EU-based samples) or the QIMR Berghofer (for AUS-based samples) at visits V5, V9, and V13 for all informative patients.

3.3 Telomere length & telomerase profiling

Analyses of telomere length from mononuclear cells, will be performed using a ddPCR-based assay at the Leipzig laboratory (for EU-based samples) or the QIMR Berghofer (for AUS-based samples) at baseline, visit V9 (assessment of primary end point) and at EOT. Analyses of telomerase (hTERT) gene polymorphisms will be performed using targeted NGS at baseline.

3.4 Additional translational analyses

BM and PB samples will be stored in a study-specific biomaterial collection to enable subsequent hypothesis-driven translational analyses, including but not limited to whole-exome/genome sequencing, transcriptome sequencing, epigenetic profiling and single cell analyses.

In Australia, patients will have their tumor tissue sent for molecular screening, using the TSO-500 NGS panel and other molecular assays, to identify clinically actionable biomarkers in tumour tissue to be used to guide treatment, and predict response. Please refer to the country specific appendix for further details.

4 Organizational and administrative aspects of the study

4.1 Investigators and study sites

Please refer to IV Contacts and responsibilities.

All other study personnel not included in this section are identified in a separate personnel list (not part of this clinical study protocol) as appropriate. This list will be updated as needed; an abbreviated version with personnel relevant for the center will be available in the center's investigator site file (ISF) and the trial master file (TMF).

Requirements for investigators and study sites

The study site will be required to have an investigator with at least 2 years' experience in conducting clinical trials according to GCP as well as a substitute with comparable qualifications. The site must have a pool of suitable patients who can be recruited for the study.

All investigators must be qualified physicians. Each physician must supply his or her curriculum vitae (updated) for the TMF.

Investigators also must

- have special experience in the study indication and respective treatment as well as diagnostic procedures,
- have a GCP certificate,
- know main features of the local legal requirements,
- know the study protocol.

The investigator must sign the separate protocol signature sheet before subject recruitment may start. Likewise, all protocol amendments must be signed and dated by the investigator before coming into effect.

4.2 Data monitoring

From the additional ■ patients that are planned to be enrolled, a risk/benefit assessment is to be performed when ■ patients have started treatment, of which at least ■ patients have completed ■ full cycles of imetelstat (after ■). This assessment will take into consideration available efficacy and safety data for these patients at that time. This data may include, for example, peripheral blast levels, WBC counts and details of AEs, SAEs and SUSARs collected in these patients. Bone marrow blast counts will also be included if available. The lead investigators in the study will analyse this data and perform the risk-benefit assessment, further details can be found in the study specific Safety Management Plan.

An independent data monitoring committee (DMC) will not be established for this study. It is deemed to not be mandatory as imetelstat has been tested in similar or more frequent dosages in previous studies and shown a generally well-tolerated and acceptable safety profile²³.

4.3 Financing

The study is financially supported by Geron Corporation.

5 Study design

5.1 Design overview

The present study is designed as a multicenter, open-label, single arm, prospective phase II study. Patients with AML or higher-risk MDS patients failing or being refractory to hypomethylating agent (HMA)-based treatment are eligible for the study. All study participants will receive the same IMP consisting of imetelstat. This section has been updated as part of a protocol amendment. Please see section 7.1.1 for details on the previous regimen and design.

Imetelstat sodium will be administered at a starting dose of ■ mg/kg given intravenously

every ■ weeks for ■ cycles of ■ days or until disease progression, unacceptable toxicity, withdrawal of consent, or lack of response. They will be assessed for response in cycle ■ according to the combined response assessment criteria for MDS and AML (Appendix III:). Non-responding patients will discontinue imetelstat treatment, undergo EOT and enter the follow-up phase of the trial. Patients who are categorized as responders based on at least PR (as described in section 2.3.1) and who have BM blasts $\geq 5\%$ at the response assessment in cycle ■ will continue to receive imetelstat every ■ weeks. Patients who are categorized as responders as per the primary endpoint definition and who have BM blasts $< 5\%$ at the response assessment in cycle ■ will continue to receive imetelstat every ■ weeks. Treatment will continue until the subject experiences unacceptable toxicities or shows loss of response/disease progression per the combined disease assessment criteria used in this trial (see Appendix III a), section 16.3), withdraws consent, or meets any other discontinuation criteria defined in section 7.7.

The design is split into two phases. At first, it was planned to enroll ■ patients in the trial. According to the initial study design, if 1 or fewer responses were seen in these patients, the study should be stopped. ■, a decision was made to amend the frequency of imetelstat administration, at least for the first ■ cycles. An additional ■ patients are planned to be enrolled ■. Please see section 1.3, section 7.6 ■ on the rationale for continuing the study and for the higher dosage justification.

Responding patients (defined as at least PR [partial remission]) are eligible to continue treatment until loss of response/disease progression.

The study will consist of a screening period, a primary treatment period (all patients), an extension treatment period (responders after 4 cycles of treatment only) and a posttreatment follow-up period. For the extension treatment period, in the absence of alternative treatment options, non-responders with stable or controlled disease may continue treatment at the investigator's discretion, in consultation with the sponsor, provided the disease remains controlled and none of the discontinuation criteria as described in section 7.7 are met.

[figure not shown]
Patients who stop the study treatment for any cause will undergo an EOT visit at the latest 14 days after the decision of treatment discontinuation. The EOT visit will be followed by a first follow-up visit (FU1) 28 ± 5 days after EOT and a second FU visit = EOS visit approximately 2 months after EOT. FU2/EOS can be carried out on the phone and represents the last study visit for the patient.

The End of Study is considered at the time the last patient completed their evaluation 6 months after the end of the primary treatment period (in case of a continued responder) or following their follow-up period (in case of a non-responder). For avoidance of doubt, for non-responders with stable or controlled disease who continue treatment at the investigator's discretion, the end of study will be defined as the end of the follow-up period for said patient or discontinuation from the trial, whichever occurs later. The sponsor will ensure that subjects benefiting from treatment with imetelstat will be able to continue treatment for as long as the subject's disease is controlled, provided that an adequate stock of imetelstat is available.

A summary of the study design is given in Figure 1.

For detailed description of study visits and procedures see VII Schedule of assessments and procedures and section 8.2.

Figure 1: Study flowchart

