7.7 Treatment discontinuation

All subjects will have an End of Treatment (EOT) visit at the time of imetelstat discontinuation. All subjects who received at least one dose of imetelstat will be followed for 3 months post last dose of imetelstat.

The following events are considered sufficient reasons for discontinuing a subject from treatment with the IMP:

- Lack of efficacy
- Adverse event
- Withdrawal by subject
- Death
- Lost to follow-up
- Pregnancy
- Protocol violation
- Study terminated by Sponsor
- Disease Progression as per combined response criteria based on IWG 2018 criteria (MDS)¹ and the criteria of the European LeukemiaNet (AML)²
- Other (to be specified on the eCRF)

The reason for discontinuation of treatment should be recorded in the eCRF and in the source documents. The decision to discontinue a subject from treatment remains the responsibility of the treating physician, which will not be delayed or refused by the sponsor. However, prior to discontinuing a subject, the investigator may contact the sponsor and forward appropriate pseudonymized supporting documents for review and discussion.

Subjects who discontinue from treatment for any reason will enter the follow-up period (for details refer to section VII Schedule of assessments and procedures and section 5.1.5 Posttreatment follow-up (FU) period).

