8.1 Description of visits

Any questions regarding the protocol should be directed to the National Coordinating Investigator or the Sponsor's Medical Expert.

All of the protocol required assessments are listed in VII Schedule of assessments and procedures.

All data obtained from these assessments must be recorded in the subject's source documentation. All study visits during the Treatment Period (both primary and extension phases) must occur within 3 days of the scheduled day.

A 5-day window is allowed for the EOT visit. If a subject is discontinued during a regular scheduled visit, all EOT procedures should be completed at that visit.

A window of ± 5 days is allowed for posttreatment FU 1 visit at which the last AE assessment will take place. The subsequent FU 2 visit (=EOS) will take place within ± 14 days of the scheduled date as described in VII Schedule of assessments and procedures.

Serum chemistry laboratory analyses, automated CBC, cytomorphology and cytogenetic analyses will all be performed locally.

Cytomorphology analyses will be carried out locally.

Refer to the eCRF completion guidelines for additional information related to data entry requirements of local laboratories.

Sample collection, processing, storage, and shipment procedures (for translational NGS analyses and study-specific biomaterial collection) will be provided in the Study Laboratory Manual.

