8.1.10 Post-treatment Follow-up Period

All subjects discontinued from protocol-prescribed therapy for any reason will be followed for a period of [REDACTED] days after the last dose of IMP for AE reporting, as well as serious adverse events (SAEs) made known to the Investigator at any time thereafter that are suspected of being related to the IMP (FU1).

Beyond FU1, all subjects discontinued from protocol-prescribed therapy for any reason should be followed for state of condition/survival until the end of the follow-up period (refer to VII Schedule of assessments and procedures, part 3).

Females of child-bearing potential (FCBP) should avoid becoming pregnant for [REDACTED] after the last dose of IMP and male subjects should avoid fathering a child for [REDACTED] after the last dose of IMP.

Data regarding subsequent MDS/AML therapies and other malignancies/pre-malignancies as well as date and cause of death, if applicable, will be recorded in the eCRF. The investigator must make every effort to obtain information regarding the subject's survival status before determining the subject is lost to follow-up. If the subject is discontinued from follow-up, the reason for discontinuation should be recorded in the eCRF at EOS.

Follow-up may be conducted by telephone contact with the subject, family, or the subject's treating physician.

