8.2.6 Follow-up assessments

8.2.6.1 Posttreatment MDS therapy and survival

Long-Term Posttreatment Follow-up for OS and data collection for subsequent MDS therapies may be conducted by record review (including public records if allowed by local regulations) and/or telephone contact with the subject, family, or the subject's treating physician. The investigator must make every effort to obtain information regarding the subject's survival status before determining the subject is lost to follow-up.

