#### **7.7.5 Overall Survival**

Overall survival (OS, in days) will be defined as the time from the beginning of treatment (date of administration at cycle ■, week ■) until date of death or censored at the date of the last observed time point alive:

In case subject dies overall survival will be:

OS [days] = date of death – Drug administration date in Visit [REDACTED] +1

Otherwise, censoring date will be:

OS [days] = Date of last observed time point alive – date of beginning of treatment +1

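### Survival contact ends about 2 months after each patient's own end of treatment, so OS censoring follows treatment failure and late Kaplan-Meier survival is likely overstated if patients die faster off treatment

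*Protocol*

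**What the plan says.** - **Last contact.** Protocol 5.1 says patients who stop for any cause "will undergo an EOT visit at the latest 14 days after the decision of treatment discontinuation", then have FU1, then "a second FU visit = EOS visit approximately 2 months after EOT". It adds that "FU2/EOS can be carried out on the phone and represents the last study visit for the patient". Protocol 8.1 gives this visit a window of plus or minus 14 days. Part 3 of the schedule collects survival status through the last follow-up column and has nothing after it; its day and week headers are redacted, so the timing here comes from 5.1.
- **Survival after FU1.** Protocol 8.1.10: patients "should be followed for state of condition/survival until the end of the follow-up period".
- **Length stated elsewhere.** Protocol 7.7: "All subjects who received at least one dose of imetelstat will be followed for 3 months post last dose of imetelstat". The synopsis time plan also gives 3 months of follow-up.
- **Long-term follow-up.** Protocol 8.2.6.1: "Long-Term Posttreatment Follow-up for OS and data collection for subsequent MDS therapies may be conducted by record review", or by telephone. It gives no duration, frequency or cut-off.
- **Censoring.** The synopsis and Protocol 2.3.2 censor OS at the last follow-up visit. SAP 6.2.2 uses the last observation in the study. SAP 7.7.5 measures OS "until date of death or censored at the date of the last observed time point alive".
- **Who stops when.** Marrow progression at the early assessment leads to EOT, as does non-response at the primary assessment, unless a non-responder with stable or controlled disease continues under Part 2c (Protocol 5.1.3). SAP 8.3 places the two assessments at weeks 9 and 17. Protocol 5.1 has continued responders evaluated 6 months after the primary treatment period.

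**The concern.** Kaplan-Meier assumes that a patient censored at a given time has the same later risk of death as those still under observation. Here censoring is triggered by treatment failure plus a fixed interval. The patients who fail first leave the risk set first, and the later part of the curve rests on responders and on non-responders judged stable enough to continue. If failure predicts death, the late curve is too high.

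The trial has no control arm, so readers will set its OS against outside figures. Protocol 1.1.1 itself quotes a median OS of 4-5.6 months after HMA failure in higher-risk MDS. SAP 8.4.1 tabulates survival at a fixed week and also for the whole study at data lock, which takes in the part of the curve most exposed to the problem.

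**Working it through.** The documents give no expected value, event count or power for OS, so there is no planned figure to reproduce.

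**1. When observation ends.** Week 9 starts on day 57 (8 x 7 + 1) and week 17 on day 113 (16 x 7 + 1). Take 2 months as 61 days.
- Week-9 progressor, EOT 0 to 14 days later: day 57 + 61 = 118 to 57 + 14 + 61 = 132, study week 17 to 19. Allowing one more week for results (an assumption): day 139, week 20.
- Week-17 non-responder who stops: day 113 + 61 = 174 to 113 + 14 + 61 = 188, week 25 to 27. With the extra week: day 195, week 28.
- Continued responder: week 17 + 26 weeks = about week 43, or longer.
- Non-responder continuing under Part 2c: later than week 28, tied to that patient's own discontinuation.

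**2. Two months or three.** FU2 falls 47 to 75 days after EOT (61 plus or minus 14). If EOT is 14 days after the last dose, FU2 is 61 to 89 days after that dose, short of 3 months (about 91 days). If EOT is 28 days after it, FU2 is 75 to 103 days after, which can reach 3 months.

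**3. Size of the bias.** Let s be the time of EOT. The death hazard is L before s and HR x L after it, so survival is exp(-L t) up to s and exp(-L s - HR x L (t - s)) beyond. L is set so that true median OS equals a chosen value in the 4-5.6 month range. Censoring is at s + 2 months. Not in the documents, and therefore assumed: HR of 1, 2, 3 or 5; 20-40% stopping at week 9; 5-20% stopping earlier; 0-20% responders, with exponential time on treatment after week 17 (mean 6 months); all others stop at week 17. Each scenario used 400,000 simulated patients.

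Each cell shows Kaplan-Meier under the plan / the same with common 12-month follow-up, which recovers true survival. Shares are given as stopping at week 9 / stopping earlier / responders.

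| True median (months); shares; HR | 4 months | 6 months | 9 months | Median (months) |
|---|---|---|---|---|
| 5.6; 30/10/5%; HR 1 | 0.610 / 0.610 | 0.475 / 0.476 | 0.330 / 0.329 | 5.60 / 5.60 |
| 5.6; 30/10/20%; HR 3 | 0.676 / 0.671 | 0.484 / 0.465 | 0.349 / 0.264 | 5.77 / 5.60 |
| 5.6; 40/20/20%; HR 5 | 0.678 / 0.670 | 0.513 / 0.467 | 0.393 / 0.268 | 6.29 / 5.63 |
| 5.6; 30/10/0%; HR 3 | 0.690 / 0.686 | not estimable / 0.462 | not estimable / 0.254 | 5.63 / 5.60 |

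For true medians of 4-5.6 months, HR 2-5 and 5-20% responders, the overstatement is at most about 1 point at 4 months, 0.6-4.7 points at 6 months and 4-13 points at 9 months; the median shifts by 0.0-0.7 months.

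A second model, with no deaths before stopping and residual medians scaled to give true medians of 18-23 weeks, overstates by at most 1 point at week 17, 0.3-4.5 points at week 26 and 2-13 points at week 39; the median shifts by 0.1-1.6 weeks. Together the two models give roughly 0.3-5 points at 6 months and 2-13 points at 9 months.

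With no responders, the result recorded at the interim in the SAP document history, the simulated curve ends at about 6 months.

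**4. Outside the cited range.** If the true median were 8 months (an assumption), the estimated median would be about 9.1-11.4 months for HR 2-5 with 5-20% responders, and not reached with none.

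**5. Three months instead of two.** With a true median of 5 months, shares 30/10/20% and HR 3, 9-month survival is 0.287 with contact to EOT + 2 months, 0.252 with EOT + 3 months and 0.207 with common follow-up. The bias falls from 8.0 to 4.5 points but remains.

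**The case against.** The strongest reply is that later survival data are already provided for. Protocol 8.2.6.1 names long-term OS follow-up by records or telephone and asks for every effort to establish survival status, 8.1.10 has date of death recorded, and SAP 7.7.5 censors at the last time point alive rather than at a visit. Record review needs no visit column. This stands in part: a reader might infer that the SAP censors at FU2, or that collection certainly stops there, and the documents do not show either. But 8.2.6.1 sets no duration or cut-off, and it does not fit 5.1, 8.1.10 or the censoring rules in Protocol 2.3.2 and SAP 6.2.2. A site following the schedule would stop at FU2.

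Second, the bias is conditional. A reader might infer that OS is always overstated. With equal hazards it is not, and no document gives the hazard after EOT. This stands.

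Third, larger figures can be produced, such as 0.47 against a true 0.32 at week 39 and a median of 34 against 27 weeks. They require that nobody dies before stopping and a true median above the range the protocol cites, and they send every week-17 non-responder who does not respond off study despite Part 2c. They do not describe the likely size.

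Fourth, the 2-month and 3-month statements might be read as a flat contradiction. They need not be: the gap between last dose and EOT decides it, as step 2 shows. The wording still needs reconciling.

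Finally, all analyses are exploratory (Protocol 10.1), there is no OS hypothesis, and the SAP survival code already requests numbers at risk. That limits the consequence but does not correct the estimate.

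**Conclusion.** The point holds in a limited form. As scheduled, OS censoring depends on each patient's own treatment failure. If mortality is higher after stopping, Kaplan-Meier OS is likely overstated, mainly after about 6 months. At true medians of 4-5.6 months, early survival and the median are little affected, while 9-month survival could be 2-13 points too high. In a cohort without responders the difficulty is not an inflated tail but a curve that stops at about 6 months.

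The sizes rest on assumed hazard ratios, stopping shares and responder time on treatment, and the 4-5.6 months is quoted for higher-risk MDS only, not AML. The bias would shrink to the extent that sites do collect later survival status under 8.2.6.1. This is a cheap improvement to a secondary, exploratory endpoint; it does not touch the primary analysis.

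**What to change.** 1. In Protocol 5.1, 8.1.10, 8.2.6.1 and Part 3 of the schedule, state that vital status and date of death are obtained for every treated patient at one common cut-off, for example the last patient's end of study, by the telephone contact or record review that 8.2.6.1 already permits. For patients already past FU2, obtain status retrospectively where consent and local rules allow.
2. Align the OS censoring text in the synopsis, Protocol 2.3.2 and SAP 6.2.2 with SAP 7.7.5: last date known alive, up to the common cut-off. SAP 7.7.5 needs only the cut-off added.
3. Reconcile the follow-up length in the synopsis time plan and Protocol 7.7 with that in 5.1.
4. Report numbers at risk and reverse Kaplan-Meier follow-up by cohort.

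If status cannot be obtained for some patients, caution against reading the late part of the curve. OS should not be cut off at the earliest censoring time, because that discards valid data.

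Cost: one contact or record check per surviving patient, a short amendment and a consent check. No visit or procedure is added. Access to public records depends on local rules.
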